9.4.4 SAFETY ANALYSES

N/A

9.4.5 BASELINE DESCRIPTIVE STATISTICS

Intervention groups will be compared on baseline characteristics including demographics, objective and subjective sleep disturbances, cognitive impairment, depression, and anxiety.

9.4.6 PLANNED INTERIM ANALYSES

iREST Protocol IRB-5 Version 1.0 12-NOV-2020

There is no planned interim analysis for this project. The DSMB or NIMH will determine if a planned interim analysis should be conducted. If the DSMB requests a detailed safety review of SAEs or severe AEs by group, then based on that review, the DSMB or NIMH Officer will determine what steps will be taken.

[figure not shown]
9.4.7 SUB-GROUP ANALYSES

We will examine sex differences and associations with age in *a priori* subgroup analyses, but without requiring conventional statistical power.

9.4.8 TABULATION OF INDIVIDUAL PARTICIPANT DATA

Data will be stored in the long format with the end points in separate columns and participants repeated across rows specified by the time points.

9.4.9 EXPLORATORY ANALYSES

10 SUPPORTING DOCUMENTATION AND OPERATIONAL CONSIDERATIONS

10.1 REGULATORY, ETHICAL, AND STUDY OVERSIGHT CONSIDERATIONS

10.1.1 INFORMED CONSENT PROCESS

10.1.1.1 CONSENT/ASSENT AND OTHER INFORMATIONAL DOCUMENTS PROVIDED TO PARTICIPANT

Consent forms describing in detail the study intervention, study procedures, and risks will be given to the participant and written documentation of informed consent will be completed prior to starting the study intervention.

Consent Procedures and Documentation

Procedures for obtaining informed consent. During the consenting process, each prospective participant will meet in a private interview room at the study site with the PI or trained study staff. The information contained in the Informed Consent Form (ICF) is initially described orally to the prospective participant. Care is taken to inform prospective participants repeatedly that participation is entirely voluntary and that they may withdraw at any time and for any reason. Any questions will be answered. The prospective participant is then asked to read the consent form carefully. The prospective participant is asked to summarize the consent form, including the discomforts, risks, and confidentiality sections.

Enough time will be allowed for the potential participant and to make an informed decision, including time to discuss the study with the researchers and ask any questions they may have. We estimate the consenting process will take between 30 minutes and one hour. The potential participant may take the consent home to discuss with others, and return later to sign it if they desire and return at a later time to complete the study visit.

Procedures for documenting informed consent. Only after the prospective participant demonstrates by stating in their own words that they understand the purposes, risks, and potential benefits of the study and they are willing to volunteer, will the participant be asked to sign and date their respective consent forms.

A copy of the ICFs will be given to each participant. This fact will be documented in the participant's record. All original signed consent forms will be stored in the Study Consent Binder in a locked file when not in use.

Provisions for vulnerable populations. We do not anticipate any participants to fall under provisions for vulnerable populations.

10.1.2 STUDY DISCONTINUATION AND CLOSURE

The study may be discontinued at any time by the IRB, the NIMH, the OHRP, the FDA, or other government agencies as part of their duties to ensure that research participants are protected.

10.1.3 CONFIDENTIALITY AND PRIVACY

Participant confidentiality and privacy is strictly held in trust by the participating investigators, their staff, the safety and oversight monitor(s), and the sponsor(s) and funding agency. This confidentiality is extended to the data being collected as part of this study. Data that could be used to identify a specific study participant will be held in strict confidence within the research team. No personally-identifiable information from the study will be released to any unauthorized third party without prior written approval of the sponsor/funding agency.

Standard procedures for data collection will be employed to minimize the risk to participant confidentiality. An anonymous ID key will replace all details that identify participants before any use or transmission of data. Any details identifying participants will be held in confidence and stored within the secure database. The information obtained in the study will be treated in the strictest confidence and none of the participants in this study will be individually identifiable in any resulting publications or reports. All data files will be kept in password-protected computer files. All research activities will be conducted in as private setting as possible, and all confidential information gathered during the course of interviews and data collection will be entered into password-protected computers. Follow-up interactions will take place by private phone calls and emails to previously identified email addresses private to that participant.

All scanning will take place in the MRI suite in the Center for Cognitive and Neurobiological Imaging (CNI) at Stanford, to which access is restricted except to study personnel. All data will be de-identified after acquisition. PHI will be maintained in the secure REDCap database and password-protected computers in the lab of [name]. Paper copies of PHI and questionnaire data will be kept in locked cabinets in [name] lab. All computers, external hard disks, USB thumbs, tablet computer, smart phone etc. will be encrypted and password protected. Once acquired, data will be de-identified and given a generic indicator (e.g. IREST001). MRI scans, from which facial information may be reconstructed (and thus an identifier) will be de-identified using conventional face stripping algorithms for MRI data. Audio/video recordings will be edited to obscure facial features and will be marked with a generic identifier. Access to de-identified data will be available to the study personnel and access will be controlled by the study lead investigator and protocol director ([name]). All research staff will undergo training from the lead investigator, including in the means through which confidentiality is maintained.

The study monitor, other authorized representatives of the sponsor or funding agency, representatives of the Institutional Review Board (IRB), regulatory agencies or representatives from companies or organizations supplying the product, may inspect all documents and records required to be maintained by the investigator, including but not limited to, medical records (office, clinic, or hospital) and pharmacy records for the participants in this study. The clinical study site will permit access to such records.

The study participant's contact information will be securely stored in the lab of [name] for internal use during the study. At the end of the study, all records will continue to be kept in a secure location for as long a period as dictated by the reviewing IRB, Institutional policies, or sponsor/funding agency requirements.

Measures Taken to Ensure Confidentiality of Data Shared per the NIH Data Sharing Policies

It is NIH policy that the results and accomplishments of the activities that it funds should be made available to the public (see https://grants.nih.gov/policy/sharing.htm). The PI will ensure all mechanisms used to share data will include proper plans and safeguards for the protection of privacy, confidentiality, and security for data dissemination and reuse (e.g., all data will be thoroughly de-identified and will not be traceable to a specific

iREST Version 1.0 Protocol IRB-5 12-NOV-2020

study participant). Plans for archiving and long-term preservation of the data will be implemented, as appropriate.

Certificate of Confidentiality

To further protect the privacy of study participants, the Secretary, Health and Human Services (HHS), has issued a Certificate of Confidentiality (CoC) to all researchers engaged in biomedical, behavioral, clinical or other human subjects research funded wholly or in part by the federal government. Recipients of NIH funding for human subjects research are required to protect identifiable research information from forced disclosure per the terms of the NIH Policy (see https://humansubjects.nih.gov/coc/index). As set forth in 45 CFR Part 75.303(a) and NIHGPS Chapter 8.3, recipients conducting NIH-supported research covered by this Policy are required to establish and maintain effective internal controls (e.g., policies and procedures) that provide reasonable assurance that the award is managed in compliance with Federal statutes, regulations, and the terms and conditions of award. It is the NIH policy that investigators and others who have access to research records will not disclose identifying information except when the participant consents or in certain instances when federal, state, or local law or regulation requires disclosure. NIH expects investigators to inform research participants of the protections and the limits to protections provided by a Certificate issued by this Policy.]

10.1.4 FUTURE USE OF STORED SPECIMENS AND DATA

Data collected for this study will be analyzed and stored on encrypted computers and in locked files within PI [name]'s lab at Stanford. After the study is completed, the de-identified, archived data will be transmitted to and stored at the NIMH data archive, for use by other researchers including those outside of the study. Permission to transmit data to the NIMH data archive will be included in the informed consent.

[figure not shown]
With the participant's approval and as approved by local Institutional Review Boards (IRBs), de-identified biological samples may be stored in one of the National Institutes of Health (NIH) databases with the same goal as the sharing of data with the NIMH data archive. The NIH repository will also be provided with a code-link that will allow linking the biological specimens with the phenotypic data from each participant, maintaining the blinding of the identity of the participant.

During the conduct of the study, an individual participant can choose to withdraw consent to have biological specimens stored for future research. However, withdrawal of consent with regard to biosample storage may not be possible after the study is completed.

10.1.5.1 STUDY TEAM ORGANIZATIONAL STRUCTURE

The team is structured around a collaborative model. PI [name] will be the overall study PI and coordinate the data management and operations of the study.

10.1.5.2 INVESTIGATORS AND RESEARCH STAFF

10.1.5.3 PI LEADERSHIP

[name] will lead the team of investigators and staff and will direct the oversight and coordination of fiscal management, research administration, publications and data sharing, and integration of all resources needed for the project. In particular, she will (1) review and address issues that require judgment over the scientific direction and conduct of the protocol; (2) oversee decisions on any changes in research direction and therefore, have the authority to reallocate funds and resources to best meet the emerging needs of the project; (3) provide communication with in the organizational hierarchy to maintain alignment with operational priorities, and assist with addressing both scientific and implementation questions and barriers; and (4) ensure compliance with participant privacy and confidentiality regulations at all times. Decisions will be made through discussion and consensus building with all the co-investigators. Throughout the process, the PI and co-investigators will remain respectful of the perspectives that each individual brings to the project and will collaborate diligently to ensure scientific rigor and transparency and optimize operational efficiency.

10.1.5.4 RESEARCH STAFF AND POSTDOCTORAL FELLOWS

intervention implementation, (2) recruitment, retention and data collection, and (3) data management and analysis. The Intervention Implementation staff includes a clinical psychologist who will provide treatment to the participants and monitor suicide risk. The clinical psychologist will interface with the Intervention Core including Drs [name] and [name]. [name] and [name] will serve as medical-monitors for the study. The Recruitment, Retention and Data Collection staff are clinical research coordinators who will develop and implement the participant recruitment and retention protocol as well as the data collection procedures, forms and databases in the R61 phase. They will work with the Trial design and biostatistics core to refine the protocols and measures for use in the R33 phase. The two postdoctoral fellows with expertise in neuroimaging and sleep research will also contribute to data collection and ensure ongoing quality of the incoming data. The Data Management and Analysis staff will develop and maintain the data management system and protocols and perform data analyses under the guidance of PI [name] and the Trial design and Biostatistics Core.

10.1.6 SAFETY OVERSIGHT

DATA SAFETY MONITORING PLAN

This safety monitoring protocol (**Table 4**) has been successfully employed in two former randomized controlled trials for suicide prevention funded to the Co-I [DOD: W81XWH-10-2-0178, NIH: K23MH093490], and is consistent with previous and in use procedures by the research team. All procedures will be closely supervised by this study's PIs and on-site safety officers, Drs. [name] and [name]. Suicide risk assessment will be conducted using empirically-established risk categorizations (minimal, mild, moderate, severe, imminent; **Table 5**) to routinize clinical decision-making and emergency referral procedures for suicidal behaviors.

TABLE 4: DATA AND SAFETY MONITORING PLAN (DSMP)

Training of Personnel in Suicide Risk Assessment:

1. All study personnel will complete extensive clinical training in suicide risk assessment practices, led by the PI, Safety monitors, and Co-l's. This team will meet regularly to discuss suicide risk assessment, DSMP procedures, adequacy and assessment of training. Though all personnel will receive training, the CSSRS will only be administered only by Master's level staff, clinical doctoral students, or trained clinicians (PIs/Co-Is, Study Clinicians).

Primary Assessment Measure

- 2. A score ≥ 4 on the CSSRS will prompt standardized suicide risk assessment and administration of The Suicide Checklist and Suicide Assessment Decision Tree (See Below).
 - a. If risk is elevated but not imminent, established behavioral methods will be used to effectively manage risk on an outpatient basis. The PI/Safety Monitors will closely monitor decision-making and assessment, and all action taken will be clearly documented.
 - b. If risk is imminent, participants will be referred for immediate hospitalization and emergency mental health services. The PI/Co-Is will closely monitor decision-making and assessment, and action taken will be documented.

At Study Initiation:

- 3. This study will follow warm transfer procedures previously used for triage to the National Suicide Prevention Crisis Line for referral and triage. Established in 2011, this was approved by Stanford University is has been previously used in DSMP protocols conducted by the research team.
- 4. Participants will be required to provide contact information as part of informed consent procedures, including personal contact information (e.g., physical address, cell) and permission to call an identified next of kin or emergency contact in the case of an emergency. In the rare situation that: a participant is judged to be at imminent risk for suicide, is located offsite, and is unwilling/unable to seek out referred mental health services, next of kin notification will be utilized to coordinate emergency referral.
- 5. Participants will be provided with emergency referral contact information and 24-hr resources (e.g., [name], online chat and text; Crisis Text Line) for outpatient safety monitoring. Participants who endorse symptoms indicative of serious or imminent risk will be warm transferred to appropriate services.
- 6. Best practices in suicide risk assessment and management procedures will be reviewed at the outset of the study with all participants, as a central component to the informed consent process. Notification of next of kin procedures, and permission to contact this individual in event of a no-show/elevation in risk/circumstances outlined in consent form, will be reviewed prior to enrollment, in addition to confidential/non-confidential referral resources available to the participant in the event of an elevation in symptoms. Emergency resources provision will be regularly provided at the outset of participation.
- 7. Participants will be explicitly encouraged to contact the PI/Co-Is/Study Clinician if symptoms elevate between screening and intervention sessions via a 24/7 study pager.
- 8. Participants will be referred to a supervising clinician if a participant experiences distress at any point following enrollment. This will prompt standardized suicide risk assessment according to established frameworks.

Active/intervention phases of the study

- 9. No shows will be vigorously pursued.
- 10. Safety Checks will be conducted at all study visits and documented for future review.
- 11. Safety planning will be conducted if risk is judged to be elevated, prompted by standardized risk assessment findings. Safety planning will be tailored to the individual and his or her level of risk. A safety plan will be outlined via construction and use of a Coping Card. Use of Coping Cards/Collaborative Assessment and Management of Suicidal Symptoms/Safety Planning Procedures are evidence-based for the management of suicidal symptoms in outpatient settings (Joiner et al., 1999; Brown & Stanley, 2008; Jobes 2006). These list internal and external coping strategies to be implemented, should the participant experience suicidal urges at any point in the study; they also list: local community emergency mental health contact numbers, 24-hour crisis hotlines, contact information for study personnel and on-call clinicians, contact information for an identified confidant that the individual may call, should he or she experience increased distress). Lethal means restriction may be a focus of a safety plan, if and when indicated. All safety and risk assessment interactions will be closely supervised by a licensed clinician, and thoroughly documented.
- 12. 24-hr on-call clinical coverage teams will be assembled and in place throughout active treatment phases, consistent with previous IRB-approved clinical trials among high suicide risk participants (NCT01958541).Participants will be explicitly encouraged to contact the PI/Co-Is/Study Clinician if symptoms elevate between screening and intervention sessions.
- 13. Participants will be referred to a supervising clinician if a participant experiences distress at any point following enrollment. This will prompt standardized suicide risk assessment according to established frameworks.

Active/intervention phases of the study

- 14. No shows will be vigorously pursued.
- 15. Safety Checks will be conducted at all study visits and documented for future review.
- 16. Safety planning will be conducted if risk is judged to be elevated, prompted by standardized risk assessment findings. Safety planning will be tailored to the individual and his or her level of risk. A safety plan will be outlined via construction and use of a Coping Card. Use of Coping Cards/Collaborative Assessment and Management of Suicidal Symptoms/Safety Planning Procedures are evidence-based for the management of suicidal symptoms in outpatient settings (Joiner et al., 1999; Brown & Stanley, 2008; Jobes 2006). These list internal and external coping strategies to be implemented, should the participant experience suicidal urges at any point in the study; they also list: local community emergency mental health contact numbers, 24-hour crisis

iREST Version 1.0 Protocol IRB-5 12-NOV-2020

hotlines, contact information for study personnel and on-call clinicians, contact information for an identified confidant that the individual may call, should he or she experience increased distress). Lethal means restriction may be a focus of a safety plan, if and when indicated. All safety and risk assessment interactions will be closely supervised by a licensed clinician, and thoroughly documented.

17. On-call clinical coverage teams will be assembled and in place throughout active treatment phases.

TABLE 2: OVERVIEW OF SUICIDE RISK CATEGORIZATIONS

References

- Jobes DA. Managing Suicidal Risk: A Collaborative Approach. New York: Guilford Press, Inc; 2006

Multiple Attempter?

No

Elevated on Resolved Plans & Preparation

> Elevated on Suicidal Desire & Ideation

Yes

ignificant Finding

→ AT LEAST

Moderate Risk

Any Other

Yes

Any Other

→ AT LEAST Moderate Risk

EVIDENCE-BASED ASSESSMENT FRAMEWORK

- I. Previous Suicidal Behavior. Previous suicidal behavior represents the single n factor in risk assessment, distinguishing 3 clinically distinct groups:
 - a. Suicide ideators
 - b. Single attempter
 - Multiple attempters

II. The Nature of Current Suicidal Symptoms: 2 Factors

- a. Resolved Plans and Preparation. Symptoms (8): A sense of courage to m attempt, A sense of competence to make an attempt, Availability of means f Opportunity for attempt, Specificity of plan for attempt, Preparations for atterof suicidal ideation, Intensity of suicidal ideation
- b. **Suicidal Desire and Ideation.** Symptoms (9): Reasons for living, Wish to d of ideation, Wish not to live, Passive attempt, Desire for attempt, Expectanc Lack of deterrents, Talk of death
- **III. Precipitant Stressors.** Interpersonal losses (e.g., separations from loved ones) discord, Legal troubles, Physical or emotional abuse
- IV. General Symptomatic Presentation, Including the Presence of Hopelessnes diagnostic comorbidity in MDD, Alcohol use, Hopelessness
- V. Other Predispositions to Suicidal Behavior. Person-centered and background risk factors) examples: history of prior attempt (especially multiple attempts); past psychiatric history; chaotic family history, recent separation or divorce; history of sexual abuse; family history of suicide and mental illness. Demographic variable ethnicity (Caucasian or American Indian), age (elderly), gender (male), marital story or divorced). Behavioral factors: impulsivity or low impulse control

RISK CATEGORIZATIONS

Nonexistent or Minimal Suicide Risk.

No identifiable suicidal symptoms, no past of suicide attempts or intentional self-haidentifiable suicide risk factors present

Mild Suicide Risk

- 1. A multiple attempter with: no other risk factors
- **2.** A nonmultiple attempter with:
 - a. Suicidal "Desire and Ideation" of limited intensity and duration,
 - b. No or only mild symptoms of the "resolved plans and preparation" factor
 - c. No, or few other risk factors present

Moderate Suicide Risk

- 1. A multiple attempter with: any other notable finding
- 2. A nonmultiple attempter with moderate-severe symptoms of "resolved plans" facto
- 3. A nonmultiple attempter with:
 - a. No or mild symptoms of the "resolved plans and preparation" factor
 - b. Moderate-to-severe symptoms of the suicidal desire and ideation factor
 - c. At least 2 other risk factors present

Severe Suicide Risk

- 1. A multiple attempter with: any two or more other notable findings
- 2. A nonmultiple attempter with:
 - a. Moderate/severe symptoms of "resolved plans and preparation" factor an
 - b. At least 1 other risk factor present

Extreme or Imminent Suicide Risk

- 1. A multiple attempter with: severe symptoms of the "resolved plans and preparation
- 2. A nonmultiple attempter with:
 - a. Severe symptoms of "the resolved plans and preparation factor" and
 - b. At least 2 or more other risk factors present

NIH Protocol Template for Behavioral and Social Sciences Research

This study will utilize a comprehensive, in-built infrastructure and set of standard operating procedures that support safe conduct of the current trial. Based on evidence-based best practices in standardized risk assessment and management, subjects at imminent risk will be referred for immediate hospitalization. Proposed procedures have been used in previous IRB-approved proposals by the research team, and DSMP protocols employed by Drs. [name], [name], [name], [name], and [name]. If indicated by suicide risk assessment, safety monitoring will be used according to the protocol below, and treatment will be provided as an enhancement to treatment as usual (TAU). Procedures are consistent with past behavioral insomnia clinical trials among high risk participants.

DATA SAFETY MONITORING BOARD

As a further protection against risk, a DSMB will be formally constituted to: independently review, oversee, and monitor risk procedures for the proposed studies. DSMB construction will be closely guided by the PI's supervision, and consultation with Investigators and Consultants. This DSMB will report to Stanford University IRB regarding study recruitment and adverse event (AE) reporting on at least annual basis. The DSMB will consist of individuals with the following expertise, nonaffiliated with the study: (1) An expert in sleep and mood disorders, (2) A biostatistician with expertise in clinical trials, and (3) A patient advocate. During the proposed intervention, participants will be instructed to report any intervention-emergent AEs or symptoms to study Personnel. These will be closely monitored and assessed on at-least weekly basis. DSMB and Stanford IRB will be immediately advised if a participant reports a serious emerging condition or AE—independent of cause or relation to the intervention. In the rare case that an AE warrants evaluation by the ombuds/patient advocate, DSMB consensus will have power to determine appropriateness of study continuation. Such decisions will be binding.

Data Safety Monitoring Board Members:

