3.3.3 DEPRESSIVE SYMTPOMS

The BDI⁸⁹ total score after removing the sleep items will be used as the primary outcome measure of depressive symptoms. Given that suicide is a risk associated with insomnia independent of other depressive symptoms, suicidality (CSSRS and BSS) will be included as a secondary outcome measure. Given the high comorbidity between insomnia, depression, and anxiety, we will also assess anxiety using the Beck Anxiety Inventory (BAI⁹⁰) as a secondary outcome. In addition to the baseline and end of treatment assessments, the BDI, BAI, BSS and CSSRS will be assessed weekly prior to each treatment session. Additional secondary measures related to specific aspects of emotional distress relevant to depression are listed in **Table 2**.

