4.3.2 CONSIDERATION OF GENERALIZABILITY

To test the hypothesis that sleep restoration reduces depressive symptoms, it is important that the therapists remain focused on insomnia and avoid providing general psychotherapy. We will instruct the therapist to limit their interventions to the target symptoms. To that end, the therapist will not provide general psychotherapy for depression and/or anxiety. In particular, the CBT-I manual instructs the therapist to limit cognitive restructuring to sleep-related cognitions and to refrain from explicit generalization to other domains. When participants raise issues that are either outside the scope of the specific treatment or outside the scope of the study, the provider will respectfully redirect focus to sleep symptoms and treatment. The only exception is when the clinical presentation necessitates an immediate intervention, such as when the participant expresses suicidal thoughts; however, therapists will be trained to redirect this to the PI, where procedures will follow this study's DSMP. Any safety planning or referral back to the PI will be tracked for future study. Past research supports feasibility and integrity of treatment delivery using CBT-I. Our experience indicates that participants and treatment providers are able to adhere to and accept similar limits.

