6.1.2 ADMINISTRATION AND/OR DOSING

CBT-I will consist of 6 sessions administered ideally once a week over a period of six to eight weeks. A full-dose will be defined as completing all 6 sessions. Sessions will occur either face-to-face or via Stanford Zoom with a PhD/PsyD psychologist, or graduate student under the supervision of a licensed PhD/PsyD psychologist, who is experienced in administering the study treatments and has completed the CBT-I training. Study sessions will occur in treatment rooms at Stanford or via Stanford Zoom. The full description of treatment details can be found in Section 6.1.1, Study Intervention or Experimental Manipulation Description and Appendix C.

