8.2.1 QUESTIONNAIRES

Acute/Unstable Chronic Illness Is a self-administered checklist designed to reveal uncontrolled or unstable illnesses during screening. The checklist evaluates for uncontrolled diabetes, thyroid disease, kidney, prostate, or bladder conditions, congestive heart failure, angina, sever cardiac illness, stroke, cancer, asthma, emphysema, respiratory disease, chronic pain conditions such as fibromyalgia, and neurological disorders such as Parkinson's disease, and unstable epilepsy.

The Columbia Suicide Severity Rating Scale is an assessment tool the evaluates suicidal ideation and behavior. Individuals are considered high risk if they endorse a 4 and will be evaluated by study PI, Co-I clinicians, and DSMB for inclusion in this study. If individuals are considered low or moderate risk, they will be monitored over the following weeks. If individuals are considered to be of high and imminent risk, the researcher will help the participant seek immediate clinical care, either through his/her doctor or, if the doctor is not available, through local emergency services.

BDI-II Suicide item during treatment is a 21-item self-administered survey which assesses depression symptoms in the past two weeks. Item 9 of the BDI assesses suicidal thoughts and wishes. If the participant answers anything other than "0-I don't have thoughts of killing myself," study staff will ask follow-up questions and notify the clinician.

Beck Scale for Suicidal Ideation. The Beck Scale for Suicidal Ideation is an evaluation of suicidal thinking that helps identify individuals at risk. It also helps measure a broad spectrum of attitudes and

behaviors. If the participant answers anything other than "0-I don't have thoughts of killing myself," study staff will ask follow-up questions and notify the clinician.

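### Section 8.2.1 and the data and safety monitoring plan (DSMP) give research staff different instructions for a participant at imminent suicide risk

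*Combined protocol and SAP*

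**What the plan says.** The response to imminent risk is stated in these places in the combined protocol:

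- **DSMP, section 10.1.6, Table 4, item 2b:** "If risk is imminent, participants will be referred for immediate hospitalization and emergency mental health services". The text after the risk categories repeats the rule: "subjects at imminent risk will be referred for immediate hospitalization".
- **Section 8.2.1 (Questionnaires), paragraph on the Columbia scale (CSSRS):** for a person at high and imminent risk, the researcher helps the participant "seek immediate clinical care, either through his/her doctor or, if the doctor is not available, through local emergency services".
- **Section 4.3.2**, on suicidal thoughts raised in a treatment session: "therapists will be trained to redirect this to the PI, where procedures will follow this study's DSMP".
- **DSMP, Table 4, item 5:** "Participants who endorse symptoms indicative of serious or imminent risk will be warm transferred to appropriate services".

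Three further statements describe the setting. Section 3.3.3 says that "the BDI, BAI, BSS and CSSRS will be assessed weekly prior to each treatment session". Section 6.1.2 says: "Sessions will occur either face-to-face or via Stanford Zoom". Item 4 of Table 4 provides for the case in which "a participant is judged to be at imminent risk for suicide, is located offsite, and is unwilling/unable to seek out referred mental health services".

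The separate SAP does not address the point.

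**The concern.** A staff member who finds imminent risk on a questionnaire can follow section 8.2.1 and call the participant's doctor, or follow the DSMP and refer straight to hospital. Each action complies with one part of the protocol and departs from another. The section 8.2.1 route is the weaker, because emergency services come in only as a fallback.

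The stake is participant safety. The trial enrolls people with depressive symptoms and insomnia, and its own rationale links insomnia to suicide risk. Risk is screened weekly during treatment, sessions may be held by video, and the DSMP itself expects that someone at imminent risk may be offsite. At a distance, a single unambiguous rule matters most.

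**Working it through.** No arithmetic applies. The check sets the two instructions side by side, then asks whether anything reconciles or ranks them.

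| | Section 8.2.1 | DSMP, Table 4, item 2b |
|---|---|---|
| Link to the CSSRS | Endorsing a 4 means high risk | A score of 4 or more starts the standardized assessment |
| Level concerned | High and imminent | Imminent |
| Who acts | The researcher | No role named |
| First step | Participant's own doctor | Referral for hospitalization and emergency mental health care |
| Emergency services | Only if the doctor is unavailable | Part of the first step |
| Timing | Immediate | Immediate |

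**Step 1: can both rules apply to the same person?** Yes. Both start from a 4 on the same scale and both use the word imminent. Item 2b is not limited by who detects the risk.

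**Step 2: can they be read as one procedure?** Not fully. A doctor reached under section 8.2.1 might send the participant to hospital, but that would be the doctor's decision. Under item 2b the study itself makes the referral. If the doctor is available, section 8.2.1 calls for no emergency contact.

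**Step 3: does any text rank them?** Section 4.3.2 does so for therapists only. Section 8.2.1 speaks of the researcher and study staff and does not refer to the DSMP. Table 4, item 1 covers training and who may administer the CSSRS. Item 11 and the opening of section 10.1.6 cover supervision. None says which response governs.

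**Step 4: is item 5 a third route?** It need not be. A warm transfer can be a way of carrying out item 2b, so it is not counted as a further conflict.

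**Step 5: is this a damaged or superseded passage?** No. The sentences compared are complete and belong to the current text.

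**Size.** One risk level has two written routes. The documents give no rate of imminent risk, so no participant count follows.

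**The case against.** The strongest reply is that the DSMP already governs in practice. All personnel are trained in suicide risk assessment, and only Master's-level staff, clinical doctoral students or trained clinicians administer the CSSRS. A score of 4 or more leads into item 2 whoever finds it. A licensed clinician closely supervises every risk-assessment interaction, and on-call cover runs around the clock during treatment. This stands as a limit on harm: the plan does not leave an untrained person to choose a route alone. It does not settle the rule, because a supervisor reading the protocol meets the same two instructions.

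A second reply is that the CSSRS paragraph in section 8.2.1 concerns eligibility, since a person who endorses a 4 is evaluated for inclusion, and exclusion criterion 5 removes those at imminent risk. That is partly right. But the same paragraph speaks of monitoring over later weeks, and excluding a person does not say how to get that person to care.

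A third reply is that video sessions are with the therapist, for whom section 4.3.2 settles the matter. This also has force. However, the CSSRS is completed before the session, and the documents do not say that the therapist gives it or where the participant then is.

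**Conclusion.** The inconsistency is real and should be fixed. It is a safety-procedure defect at one risk level, with no bearing on the sample size, error rates or estimates. It rests on the plain wording of sections 8.2.1 and 10.1.6 and on the absence of any general statement that the DSMP takes precedence. The argument about weekly detection rests on section 3.3.3; the schedule of activities lists a different suicidality scale, the S-STS.

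A reader might infer more, but the documents do not support it:

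- **That section 8.2.1 permits delay.** It does not; it too requires immediate care.
- **That the risk scales contradict each other.** Section 8.2.1 uses low, moderate, high, and high and imminent. The DSMP uses minimal, mild, moderate, severe and imminent. The labels are not mapped, but the CSSRS value of 4 and the term imminent are common to both, and no contradiction is shown.
- **That people with past attempts escape the risk framework because attempt history is not a named trigger.** The CSSRS is described as covering behavior as well as ideation, and exclusion criterion 5 uses the standardized assessment. The gap may be nil.
- **That some symptom combinations fall in no risk category.** Item 2 names the Checklist and the Decision Tree as the tools. The tree is only partly legible in the text available, so a gap in the procedure as operated cannot be shown.

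**What to change.** Replace the risk levels and the imminent-risk response in section 8.2.1 with those of the DSMP, or add a sentence there stating that the DSMP governs. Either way, imminent risk should always lead to the item 2b response, whoever detects it and whether the participant is on site or remote. Replacing the levels also removes the unmapped labels.

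The cost is a wording change, with no new assessment, visit or staff role. The SAP, dated May 2025, reports residual checks already run, so enrollment in this phase may be over; the documents do not say. If it is, the correction belongs in any reuse of this text for the planned 150-participant R33 trial.
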